6.2 Treatment Targeting Volume

6.2.1 Metastasis location

Because of the potentially increased risk of pneumonitis from combining SBRT with nivolumab, conservative SBRT planning is recommended for lung lesions. A tight dose constraint for lung ($V_{20} < 4\%$ with mean lung dose $< 4\text{Gy}$) is required to minimize the risk of radiation pneumonitis¹⁰⁹ (Table 6.5.5-1).

Lung Central: Central lung tumor is defined as GTV within 2 cm of proximal bronchial tree as described in RTOG 0813/0915:

Tumor within or touching the zone of the proximal bronchial tree, defined as a volume 2 cm in all directions around the proximal bronchial tree (carina, right and left main bronchi, right and left upper lobe bronchi, intermedius bronchus, right middle lobe bronchus, lingular bronchus right and left lower lobe bronchi). [See Figure 6.2.1-1]

mediastinal or pericardial pleura (PTV touching the pleura) also are considered central lung tumors. A visual representation is shown below in Figure 6-1.

Lung Peripheral: Metastases within the lung parenchyma with GTV outside of the proximal bronchial tree as described above.

Mediastinal: GTV arising within the anatomic space between the lungs, above the diaphragm, and below the thoracic inlet at the level of the top of the sternal notch. Sternal metastases will be assigned to the mediastinal location based on potential for normal tissue toxicity.

Head and Neck: GTV occurring within head and neck parenchyma or cervical lymph node Levels I-VI and/or retropharyngeal spaces.

Liver: GTV arising within the liver. Rib or skin lesions immediately adjacent to the liver will be assigned to the liver metastasis location.

[figure not shown]

Fig 6.2.1-2. Diagram of Spine Metastasis and Target Volume

Spinal: Metastases will be assigned to the spinal/paraspinal site if the GTV arises within the vertebral bodies expanded by 1 cm. Spinal metastases, shown in Figure 6-2 in black, can involve:

- The vertebral body only OR
- The vertebral body and pedicle OR
- Posterior elements only

For each of these metastases, the PTV delineation will include:

- the involved vertebral body and both pedicles (solid red line in Figure 6.2.1-2a) OR
- a more generous delineation of the involved vertebral body and both pedicles (dashed red line in Figure 6.2.1-2b) OR
- the involved vertebral body, both pedicles, and the anterior and posterior elements of the spine (solid red line in Figure 6.2.1-2b) OR
- the spinous process and laminae (solid red line in Figure 6.2.1-2c)

The target volume may be chosen at the discretion of the treating Radiation Oncologist based on the extent of tumor involvement.

Metastases arising in the ribs within 1 cm of the edge of the vertebral body should be included in the spinal metastasis location but osseous metastases planning guidelines are to be used.

Osseous: GTV arising within an osseous structure, part of the axial skeleton, not included in the

spinal definition.

- Rib metastases that are within 1 cm of the vertebral bodies will be classified into the spinal metastasis location given the similar normal tissues at risk.
- Rib/scapular metastases within the thorax adjacent to lung parenchyma will be classified into the lung metastasis location given the similar normal tissues at risk.
- Rib/osseous metastases adjacent to mediastinal or cervical structures will be classified into the mediastinal/cervical lymph node location given the similar normal tissues at risk.
- Rib metastases adjacent to the liver will be classified into the liver location given the similar normal tissues at risk
- Rib metastases adjacent to the stomach/abdominal wall will be classified into the intra-abdominal location given the similar normal tissues at risk
- Sternal metastases will be considered part of the mediastinal/cervical lymph nodes location given the similar normal tissues at risk.

Abdominal-pelvic: GTV arising within the anatomic space defined by the diaphragm superiorly, the genitourinary diaphragm inferiorly including the peritoneal and retroperitoneal spaces, not including liver, osseous, or spinal metastases.

Skin: GTV arising within the skin or the underlying subcutaneous tissue. If the volume of GTV mandates photon beams for treatment, the lesion will be considered part of the neighboring anatomic location.

Extremities: GTV arising within the upper and lower extremities.

6.3 Dosimetry

6.3.1 Target Volume Definition Based on Metastatic Location

Specific SBRT planning parameters depend on the location of the treated metastasis as well as mechanism used for motion management/evaluation. In general the GTV is defined as the entirety of the primary or metastatic lesions as seen on planning CT scan aided by additional diagnostic imaging studies (i.e., PET/CT or MRI). Use of additional diagnostic studies is left to the discretion of the treating physician. The CTV=GTV; there is no margin added for microscopic extension. In general, either a helical CT or 4DCT will be used for defining the GTV/ITV depending upon the tumor motion encountered, although both scans may be acquired at the time of simulation. Typically, the ITV is generated using either expiratory/inspiratory phase scans or from reconstructed maximum intensity projection (MIP) scans. Maximum/minimum intensity projections (MIP/MinIP) should be used with caution because the MIP reconstruction for lung or MinIP reconstruction for liver may erroneously define an ITV in cases of significant irregular breathing or when tumors abut soft tissue structures (e.g., the diaphragm for MIP) or fat (for the MinIP).

[figure not shown]
- A GTV to ITV expansion of greater than 1cm in any one direction is strongly discouraged and alternative respiratory management technique is suggested.
- When osseous/rib or skin metastases are classified into other specific metastatic locations, the planning guidelines for that metastatic location should be used. If rib metastases are grouped into the spinal metastasis location, then the metastasis should be contoured as defined for osseous metastases, but the prescription doses for the spinal region should be used.

- Mediastinal lymph nodes should undergo motion assessment and an ITV should be generated to account for motion.
- In general CTV/ITV to PTV expansion will include 5mm circumferential margin and 7mm craniocaudal margin, but may be modified at the treating physician's discretion.

6.3.2 Planning Techniques

General Considerations: A variety of planning techniques can be used to deliver SBRT for each metastasis. General guidelines include the following:

- Multiple coplanar or non-coplanar beam arrangements are acceptable.
- Typically 7-13 static radiation beams with equal weighting are used. It is recommended that at least 10 beams be used when possible.
- A minimum field dimension of 3 cm should be observed treating small metastases.
- Dynamic conformal arcs are acceptable. It is recommended that arcs span at least 340 degrees.
- For non-IMRT or dose painting techniques, the conformal field aperture size and shape should correspond nearly identically to the projection of the PTV along a beam's eye view (i.e., no additional "margin" for dose buildup at the edges of the blocks or MLC jaws beyond the PTV). The only exception will be when observing the minimum field dimension of 3 cm when treating small lesions.
- The prescription isodose line covering 95% the PTV will generally be 80-90% but may range from 60-90% where the maximum dose is 100%. As a result, a "hotspot" will exist within the PTV that is equal to the prescription dose divided by the prescription isodose line (i.e., $24\text{Gy}/0.6 = 40\text{Gy}$ when 24Gy is prescribed to the 60% isodose).
- Doses higher than the prescription isodose (i.e., hotspots) should be manipulated to occur within the target.

Dose calculations: All dose distributions shall include corrections for

tissue heterogeneities. IROC Houston approved algorithms must be used. All doses should be reported in terms of dose-to-water and not in terms of dose-to-medium.

Successful treatment planning will require accomplishment of all of the following criteria: These criteria will be assessed on dose calculated independently for each metastasis (i.e., not from composite dose calculations)

- Normalization: The treatment plan should be initially normalized such that 100% corresponds to the maximum dose within the PTV (MAXPTV). While this point will typically correspond to the PTV center of mass, it can be located elsewhere within the PTV.
- Prescription Isodose Surface Coverage: The prescription isodose surface will be chosen such

that 95% of the target volume (PTV) is conformally covered by the prescription isodose surface. Doses less than 95% of the prescription dose are restricted to the outside edges of the PTV as shown in Figure 6-3. The prescription isodose surface selected MUST be $\geq 60\%$ and $\leq 90\%$ of the dose maximum within the PTV (MAXPTV). The MAXPTV corresponds to the normalization point (100%) of the plan as noted in number 1 above.

- Target Dose Heterogeneity: Rather than prioritizing target dose homogeneity, SBRT treatment planning prioritizes adequate minimum target coverage and rapid dose fall-off gradients outside of the target. Hot spots within targets are generally accepted without consequence since targets are mostly tumor. The only exception is when the hotspot within the PTV also intersects an OAR (see Figure 6.3.2-1).
- Critical Organ Doses: Respect all critical organ dose-volume limits listed in Section 6.5) below
- High-Dose Spillage:
 - Location: Any dose $> 105\%$ of the prescription dose should occur within the PTV and not within the normal tissues outside the PTV. See Figure 6.2.3-1.
 - Volume: Acceptable isodose distributions should be as conformal as possible. To this end the ratio of prescription isodose volume to PTV should be as small as possible.
 - ◆ The ratio of the prescription isodose volume to the PTV volume should be < 1.2 . Acceptable variations include a ratio of 1.2-1.5. Ratios above 1.5 will be considered unacceptable variations. The prescription line for each lesion will be contoured for calculation of this ratio. The prescription line will be labelled as V_24. Contours with identical doses should be distinguished according to the convention described in section 6.5.
 - ◆ Guidelines for the ratio of the 50% prescription isodose volume to the PTV volume (R50%) and for the maximum dose at 2cm (D2cm) from the PTV are given in Table 6-4. Because it may become more difficult to restrict the 50% isodose volume when dose is summed from treatment of multiple metastases, this ratio should be evaluated for dose calculated for a single metastasis (i.e., not for composite dose). Additionally, the 50% isodose volume may be elongated deliberately in order to avoid OAR thereby making it difficult to meet the guidelines in Table 6-4. This is acceptable as long as normal tissue constraints are met.
 - ◆ Given that conformal tumor coverage is often more difficult to achieve in lung than in more homogeneous organs, these ratios should serve as a guide for liver, abdominal-pelvic, mediastinal/cervical metastases as well.
 - ◆ Elliptically shaped metastases as well as extremity metastases may not meet these guidelines. This is acceptable as long as normal tissue constraints are respected.
 - ◆ These criteria will not be required in treating very small tumors (< 2.5 cm axial GTV dimension or < 1.5 cm craniocaudal GTV dimension) in which the required minimum field size of 3 cm (see Section 6.2) results in the inability to meet a conformity ratio of 1.5.

Table 6.3.2-2

PTV Volume (cc)	Ratio of 50% Prescription Isodose Volume to PTV Volume, R50%	Maximum Dose at 2cm (D2cm) from PTV in any direction as % of Prescribed Dose
1.8	< 7.5	<57.0
3.8	< 6.5	<57.0
7.4	< 6.0	<58.0
13.2	< 5.8	<58.0
22.0	< 5.5	<63.0
34.0	< 5.3	<68.0
50.0	< 5.0	<77.0
70.0	< 4.8	<86.0
95.0	< 4.4	<89.0
126.0	< 4.0	<91.0
163.0	< 3.7	<94.0

NOTE: For values of PTV dimension or volume not specified, linear interpolation between table entries is required.

NOTE: For tumors within 2 cm of the skin, it may be difficult to meet the values for D2cm and R50%. In these cases, these criteria will not be used.

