When using a gantry mounted linear accelerator for this protocol, the isocenter is defined as the common point of gantry, collimator, and couch rotation for the treatment unit. For other types of treatment units (e.g., Tomotherapy or CyberKnife), a reference point in space that is typically positioned at the center of the target is used instead of a mechanical isocenter.

When treating multiple lesions, it is best to use multiple isocenters, each centered on a separate lesion. Treating different targets on different days is allowed in order to decrease treatment time for a single day. For widely spaced lesions (over 10 cm apart), localization is improved when the isocenter is placed in the center of each target and image guidance is performed individually for each target. This is due to the limitation of most IGRT systems which ignore necessary rotational corrections when table shift coordinates are derived. Some platforms, including Cyberknife and Tomotherapy, are inherently non-isocentric. These platforms take special account in the setup and treatment process to rigorously detect and account for rotations to avoid errors making them exempt from the separate isocenter for each lesion requirement. For other platforms, the use of a single isocenter to treat multiple lesions in proximity to each other may be allowed if the institution has credentialed successfully for SBRT treatment of 2 lesions with a single isocenter setup.

Composite Dose Calculations

Composite plans should be generated to incorporate the dose to surrounding normal tissues from each metastasis treated. The composite doses to critical normal tissues will be used to evaluate plan compliance. Composite planning refers to dose summation from multiple treatment sites on a single CT scan that encompasses the relevant anatomy. Composite treatment planning is best accomplished by obtaining a planning CT dataset that incorporate all targets and relevant critical structures in the imaging study. If this is not possible due to restrictions on the size of the imaging study that can be

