The minimum IGRT requirement for each metastatic location is listed in Table 6-2. Volumetric imaging refers to 3D modalities (e.g., kV cone-beam, MV cone-beam, CT on rails) while orthogonal imaging refers to 2D modalities (e.g., kV OBI, ExacTrac). For volumetric imaging, appropriate CT window/level thresholds must be employed for registration at each metastatic location as outlined in Table 6-3. Additional IGRT may be employed at the discretion of the treating physician (i.e., orthogonal kV imaging prior to required volumetric imaging or volumetric imaging even if only orthogonal kV imaging is required). Note that when orthogonal kV imaging is employed for sites where respiratory motion is expected and not controlled via motion management techniques, care must be taken to ensure accurate targeting of the ITV within the treatment. For example, static kV imaging at an undetermined breath hold position would not be adequate IGRT for treating a free-breathing lung tumor.

Use of a shortened CT planning scan for registration may be important for IGRT systems that cannot handle a large number of CT slices. A subset of the planning CT scan can be uploaded to the IGRT system for localization of each metastasis. The CT data should include the metastasis of interest plus at least 5cm superiorly and inferiorly. Please note that composite dose must be calculated on a single CT scan encompassing all pertinent OAR.

Table 6.1-1

Metastatic Location	Minimum IGRT Requirement	
	No Fiducials	With Fiducials**
Lung--Peripheral ⁺	Volumetric (3D)	Orthogonal kV (2D)
Lung—Central ⁺	Volumetric (3D)	Orthogonal kV (2D)
Mediastinal/Cervical LN	Volumetric (3D)	N/A
Liver ⁺	Volumetric (3D)	Orthogonal kV (2D)
Spinal	Orthogonal kV (2D)	Orthogonal kV (2D)
Osseous*	Orthogonal kV (2D)	N/A
Abdominal-pelvic ⁺	Volumetric (3D)	Orthogonal kV (2D)

*NOTE: When osseous/rib metastases are classified into another metastatic location, follow the IGRT guidelines for that site.

**NOTE: When a metastasis contains an implanted fiducial that is clearly visible on kV orthogonal or volumetric imaging, either method can be used

+NOTE: Registration using a soft tissue surrogate for the tumor is recommended for lung, liver, and abdominal-pelvic metastases for both 3D and 2D IGRT datasets.

Fig 6.2.1-1. Central lung definition.

[figure not shown]

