6.5.5 Critical Organ Dose-Volume Limits

Composite dose plans including all treated metastases and organs at risk are recommended to minimize toxicity from the field overlap. To facilitate composite planning, dose to all metastases should be calculated on a single CT scan simultaneously with in-plane resolution of at least 3 x 3 x 3mm. If this is not possible, composite plans should be generated incorporating the dose from each metastasis treated. The composite doses to critical normal tissues will be used to evaluate plan compliance.

Tables 6.5.5-1 lists maximum dose limits to a point or volume within several critical organs based on the 3 fraction SBRT.

The spinal cord doses are absolute limits, and treatment delivery that exceeds these limits will constitute a major protocol violation. However, some OAR (ie, the esophagus, trachea, bronchi and heart within the lung) may be situated adjacent to the treated GTV/PTV. As such, there is no specified limit as tumors that are immediately adjacent to that organ will not be able to be treated to any of the prescription doses without irradiating a small volume of that organ to the prescribed dose. In such a case, the planning needs to be done so that there is no hot spot within that organ, even if that organ is part of the GTV, PTV, i.e., that no part of any OAR receives more than 105% of the prescribed dose. In addition, the volume of the OAR in question needs to be minimized, both in length and in the width (i.e., circumference), with efforts made to reduce the dose to the contralateral wall of the organ.

For non-spinal cord organs at risk with known sensitivity to high doses of radiation (including the bowel, esophagus, and stomach) included within a PTV or immediately adjacent to PTVs, a prescription dose at the lower end of acceptable variation should be used. Additionally, every effort should be made to cover the GTV with the prescription dose while ensuring rapid falloff to the organ at risk. Coverage of a section of PTV including or immediately adjacent to the OAR may be as low as 70% of the prescription dose ONLY in this situation. Every effort should be made to cover 100% of the GTV by the prescription dose at the lower end of acceptable variation. Since the tumor and normal tissue may not allow strict avoidance, the larger volume limits will not be scored as protocol Deviations Unacceptable if exceeded.

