6.7 Compliance Criteria

Treatment Duration

Per Protocol: Treatment should be completed within 2 week. Acceptable Variation: Treatment completing >2 but < 3 weeks Unacceptable Deviation: Treatment completed > 4 weeks

PTV Dosimetry Compliance

A single prescription, 24Gy in 3 fractions, will be used for all tumor lesions receiving SBRT. Simultaneous integrated boost planning can be utilized to achieve this dose to a partial tumor volume when near a critical organ at risk. Acceptable variation in this clinical scenario is to deliver at least 7Gy per fraction to the 95% of GTV

Organ at Risk Dosimetry Compliance

Respect spinal cord, cauda equina, sacral plexus and brachial plexus dose constraints. Any dose to spinal cord, cauda equina, sacral plexus above that listed in Tables 6.5.5-1 will be considered an unacceptable deviation. For all other OAR, when OAR dose criteria provided in Section 6.5 cannot be accomplished by following planning priorities outlined in Section 6.4, doses to serial OAR of more than 105% of the dose prescribed to the PTV will be scored as unacceptable deviations. Doses to parallel OAR exceeding 110% of the dose prescribed to the PTV will be scored as unacceptable deviations

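### Section 6.3.2 lists critical organ doses among criteria judged one metastasis at a time, while 6.1.2.1 and 6.5.5 judge organ limits on composite dose

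*Combined protocol and SAP*

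**What the plan says.** Section 6 allows one to four irradiated metastases per Arm B patient. Section 6.3.2 gives a list of criteria, all of which a plan has to meet, introduced by this rule: "These criteria will be assessed on dose calculated independently for each metastasis (i.e., not from composite dose calculations"). The list covers normalization, prescription coverage, target heterogeneity, organ doses and spillage. Its organ item reads: "Critical Organ Doses: Respect all critical organ dose-volume limits listed in Section 6.5".

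Section 6.1.2.1, under its composite-dose heading, states: "The composite doses to critical normal tissues will be used to evaluate plan compliance". Section 6.5.5 repeats that sentence. Section 6.5.5 also says: "Composite dose plans including all treated metastases and organs at risk are recommended to minimize toxicity from the field overlap".

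Table 6.5.5-1 limits mean lung dose to <4 Gy and the lung volume at 20 Gy to <4%. It limits cord to 18 Gy (<0.03 cc) and 13 Gy (<1.2 cc). On cord, 6.5.5 adds: "The spinal cord doses are absolute limits, and treatment delivery that exceeds these limits will constitute a major protocol violation". Section 6.7 adds: "Any dose to spinal cord, cauda equina, sacral plexus above that listed in Tables 6.5.5-1 will be considered an unacceptable deviation". For parallel organs such as lung, 6.7 says: "Doses to parallel OAR exceeding 110% of the dose prescribed to the PTV will be scored as unacceptable deviations".

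**The concern.** For organ limits the two rules are opposite. No sentence exempts the organ item from the 6.3.2 lead-in or says which section prevails. Normal tissue receives the sum of the doses from all treated lesions, so a lesion-by-lesion check is the wrong check whenever two lesions share an organ.

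The wording of 6.5.5 adds to the ambiguity. It only recommends composite plans, yet two sentences later in the same paragraph relies on composite dose to judge compliance. A site could cite 6.3.2 together with that weaker word to justify checking organs one lesion at a time.

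What is at stake is planning safety in Arm B. Section 6.2.1 makes the tight lung constraint mandatory because adding SBRT to nivolumab may raise the risk of pneumonitis. Pneumonitis and myelitis are two of the three radiation toxicities named for the interim safety review in 4.1.

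**Working it through.** **Which basis is intended.** Three places bear on this.

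- Section 6.4 ties single-lesion assessment to dose compactness (coverage, spillage, D2cm, R50%) and ranks organ constraints as separate priorities.
- Section 6.3.2 gives its own reason for scoring R50% per lesion: the 50% isodose volume is harder to restrict once doses are summed. That reason concerns spillage and does not carry over to organ tolerance.
- Sections 6.1.2.1 and 6.5.5 both evaluate compliance on composite dose.

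All three point to composite dose for organs. The per-metastasis lead-in fits every item in the 6.3.2 list except the organ one.

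**What a literal reading lets through.** The protocol gives no per-lesion organ doses, so those below are assumptions for illustration. The limits come from Table 6.5.5-1 and the prescription of 24 Gy in 3 fractions from 6.1.1.

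1. Mean lung dose. The lung volume is the same for each lesion's plan, so the means add. Two lesions at 3 Gy: 3 + 3 = 6 Gy against <4 Gy, and 6/4 = 1.5 times the limit. Each lesion passes alone.
2. Equal-share threshold, 4/k Gy for k lesions. The sum exceeds 4 Gy once each lesion gives more than 4/2 = 2.0 Gy, 4/3 = 1.33 Gy or 4/4 = 1.0 Gy.
3. Lung volume at 20 Gy. Two lesions each taking 3% of lung, in volumes that do not overlap: 3% + 3% = 6% against <4%. Each passes alone.
4. Cord, if both plans dose the same point. 10 + 10 = 20 Gy against 18 Gy. The equal-share threshold 18/k is 9, 6 or 4.5 Gy for two, three or four lesions.

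**Whether 6.7 would catch it.** For parallel organs the scoring threshold is 1.10 × 24 = 26.4 Gy. A mean lung dose of 6 Gy is far below that, so this scoring would not flag item 1. For cord, 6.7 scores any dose above the table and 6.5.5 calls an excess a major violation, so item 4 is covered.

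There is no stated figure in the plan to reproduce, and no power, alpha or sample-size quantity is involved.

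**The case against.** The best defence is that the rest of the protocol already supplies the right answer. The 6.3.2 criteria are necessary, not sufficient, so passing them lesion by lesion does not approve a plan. The organ item itself sends the reader to Section 6.5, where 6.5.5 applies composite dose. Section 6.1.2.1 gives detailed instructions for summing dose, and 6.5.5 makes calculating all lesions together on one scan the default. A physicist who reads the whole of Section 6 would use composite dose. All of this stands, and it limits the consequence. It does not remove the contradiction, because no sentence ranks the rules.

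Four stronger readings are tempting, and the documents do not support them.

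- *The protocol accepts over-limit plans.* It does not. Section 6.3.2 on its own fails to reject them, but 6.1.2.1 and 6.5.5 still apply.
- *An excess would be found only after delivery.* Both composite sentences speak of plan compliance, and nothing says the check comes after treatment.
- *Cord could receive about 1.8 times its limit.* Take two 34 cc PTVs at the 68% D2cm ceiling in Table 6.3.2-2. Each gives 0.68 × 24 = 16.32 Gy at 2 cm, and 2 × 16.32 = 32.64 Gy at a cord point 2 cm from both. This ignores the 13 Gy (<1.2 cc) cord row, which 16.32 Gy may already break singly, depending on the cord volume involved. It also ignores the R50% guideline in the same table row. That caps the 12 Gy volume at 5.3 × 34 = 180 cc, a sphere of radius 3.50 cm. The PTV radius is 2.01 cm, so the 2 cm point lies 4.01 cm from the centre. With spherical, concentric volumes each lesion gives less than 12 Gy there, and two give less than 24 Gy. An excess over 18 Gy remains possible, but the 32.64 Gy figure should not be used.
- *Section 6.1.2.1 flatly mandates composite dose.* Its sentence "Please note that composite dose must be calculated on a single CT scan encompassing all pertinent OAR" closes a paragraph on shortened registration scans. It specifies which scan to use, and is not a clear requirement to produce a composite plan.

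**Conclusion.** The contradiction is real and visible in the text, and the organ item is misplaced. Its practical weight is small. It matters only for Arm B patients with two or more treated lesions close enough to share an organ, and the documents do not say how many there are. A single-lesion plan is unaffected.

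Lung is the less protected organ. On the assumed doses, a mean lung dose of 1.5 times the limit passes a literal 6.3.2 check and draws no unacceptable-deviation score under 6.7, although 6.5.5 would still find it over the limit on composite dose. Cord excess is already a violation.

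The dose figures are illustrations that rest on simple addition, with a shared point for cord and non-overlapping volumes for the 20 Gy lung limit. They are not expected doses, and no plan is shown to have been misjudged. The primary endpoint, sample size and error rates are not affected. This is a minor safety clarification.

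**What to change.** In 6.3.2, restrict the per-metastasis rule to normalization, coverage, heterogeneity and spillage. State that the Table 6.5.5-1 limits are assessed on composite dose as set out in 6.1.2.1 and 6.5.5.

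In 6.5.5, change composite plans from recommended to required when more than one lesion is treated. The justification is 6.5.5's own use of composite dose to evaluate compliance. The scan-selection sentence in 6.1.2.1 is not needed for this.

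The cost is two wording edits in an amendment. No new procedure follows, since 6.1.2.1 and 6.5.5 already judge compliance on composite dose. Optionally, composite lung and cord dose could be checked on stored multi-lesion plans. With approximately 50 subjects randomized 1:1, that is at most about 25 Arm B patients. If Arm B planning is already finished, this check is where the remaining value lies.
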